1.0 Objectives

- 1.1 Assess the use of implanted fiducial markers in the treatment planning and delivery workflow for frame-based spinal stereotactic body radiation therapy (spinal SBRT).
- 1.2 Characterize the six-dimensional set-up accuracy of the ExacTrac patient positioning system as applied to spinal SBRT for lesions of the thoracic and lumbar spine.
- 1.3 Establish whether the addition of implanted gold seed fiducials enhances the ability of the ExacTrac system to detect and correct patient position relative to image fusion based solely on bony anatomy.
- 1.4 Characterize the radiation dose delivered to organs at risk (OARs) when accounting for intrafraction OAR motion through the use of 4 dimensional CT simulation for treatment planning.
- 1.5 Characterize the radiation tolerance of the normal esophagus to large-fraction radiation treatment through dose constraint relaxation.

2.0 Background

Spinal metastases represent a common site of metastasis, representing up to 70% of all bony metastases (1). In addition to pain caused by bone destruction or pathologic fracture, metastases to the vertebral column pose the additional threat of progressive neurological morbidity from epidural cord compression; 8-20% of patients with spinal metastases will

develop symptomatic cord compression. Radiation therapy has a well-established role in the management of spinal metastases, but the efficacy of conventional radiation therapy is ultimately limited by the tolerance of the spinal cord. Stereotactic radiation techniques for spinal metastases circumvent this limitation, using a combination of stereotactic localization and intensity modulation to precisely deliver highly conformal treatments.

Spinal SBRT is a non-invasive treatment for spinal metastases which achieves a high probability of local tumor control by conformal administration of hypofractionated radiation with submillimeter precision. This approach carries several advantages, including greater efficacy for radioresistant histologies (e.g., renal cell carcinoma or melanoma (2-4) and the ability to offer a short course of treatment (typically 1-3 fractions) in the palliative setting. First clinically applied to 5 patients using a skeletally fixed stereotactic frame in 1995 (5), the clinical literature now describes some 700 patients, with over 900 lesions treated with stereotactic radiotherapy (6). With growing clinical experience, it has become clear that the outcomes from spinal SBRT are excellent: ~80-90% actuarial 1 year local control (7-9) and successful palliation in 85-90% of patients (7, 10, 11). The hypothesis that spinal SBRT can provide superior pain control is currently under formal investigation in RTOG 06-31 (12), which randomizes patients to SBRT (16 Gy in 1 fraction) vs. 8 Gy in 1 fraction.

While spinal SBRT is an emerging modality with maturing follow-up data, its widespread clinical adoption is still relatively recent, and, as such, there are still a multitude of questions as to best practices for use of this modality. A chief limitation of spinal SBRT is the technical expertise required to safely and effectively administer the treatment. Treatment delivery systems employ stereotactic immobilization with image guidance, and require extreme accuracy and meticulous attention to detail – several groups have published the technical details

of their approaches (13-15). A commonality among these approaches is the use of two-dimensional patient alignment techniques, followed by three dimensional imaging to assess patient set-up at the time of treatment (e.g. cone-beam CT, CT-on-rails), as defined by 3D-3D matching of the CT simulation dataset to the daily verification imaging . However, with the advent and adoption of advanced patient positioning systems, e.g. ExacTrac (BrainLab), it remains unclear whether new alignment technologies obviate the need for the latter step of 3D-3D verification. Furthermore, the extent to which these systems can account for rotational set-up error is not completely understood.

We have thus designed this protocol to address these gaps in current clinical knowledge. Broadly, our protocol first seeks to combine implanted gold fiducials, four-dimensional treatment planning, and CT-on-rails capability at the time of treatment delivery to establish a platform for obtaining very precise measurements of patient position and dose delivered. With this tool in hand, we next seek to obtain high quality data on the radiation tolerance of esophageal tissues to large fractions of radiation, through gradual constraint relaxation and prospective toxicity monitoring.

2.1 Characterizing geometric uncertainty in treatment delivery

For spinal SBRT, accuracy in patient positioning is the cornerstone of providing safe and high quality treatment. Previous work from our institution underscored the importance of precise patient set-up, permuting delivered treatment plans to account for potential setup error, and demonstrating that a 2mm translational error can lead to >5% loss of tumor coverage, and greater than 25% increase in the maximal dose to the organs at risk (16).

Our current practice employs the Brain Lab ExacTrac targeting system (17, 18) which uses floor-mounted kV imagers to acquire a pair of orthogonal oblique films, which are used

(sometimes in conjunction with external locator devices) by the system software to compare the patient's position relative to the treatment planning dataset on the basis of bony anatomy. Based on this software fusion, the system calculates the required couch shifts to achieve optimal patient alignment, which are executed through a robotic couch system. Next, the coordinates of the final isocenter are verified using a CT-on-rails system to acquire a three-dimensional dataset. In-house software (19) is used to perform a 3D-3D fusion of the datasets, which then allows computation of the deviation from the planning CT, with tolerances for translation and rotational error of 1 mm and 2 degrees, respectively. Our current practice thus uses the ExacTrac system software to calculate the necessary couch corrections based on algorithmic alignment of bony anatomy alone. However, the ExacTrac software also has the capability calculate patient position based on implanted fiducial markers, provided that the markers are present at the time of CT simulation. Based on our extensive experience with the ExacTrac system, we observe that the bony fusion based calculations excel at detecting translational set-up errors, but can yield discrepancies in assessing rotational error (roll, pitch, yaw). We hypothesize that the addition of implanted fiducials will improve setup accuracy, particularly with regard to rotational error.

The incorporation of implanted fiducials would thus allow us to address two important questions. Firstly, by having the ExacTrac software calculate the required couch corrections with and without consideration of the fiducial markers, we will be able to assess whether the use of implanted fiducials enhances the accuracy of the ExacTrac fusion as compared to fusion based on bony anatomy alone, verified by CT-on-rails. Secondly, the presence of fiducial markers will allow a more accurate comparison of the verification CT dataset with the planning CT, thus allowing us to assess whether our current practice of final 3D-3D verification is necessary.

The use of implanted fiducial markers has been well established in other radiation therapy platforms, including use in image guided radiation therapy for prostate cancer (20) or SBRT for liver disease (21). With respect to spinal SBRT, the Cyberknife platform for stereotactic treatment delivery uses implanted fiducial markers as part of a frameless treatment delivery system (10, 22).

While implanted gold seeds are commonly and safely used for multiple indications, and frequently utilized in clinical spinal SBRT practice, the use of implanted fiducials for patient setup analysis in frame-based spinal SBRT has not been well reported in the clinical literature. A pilot study at the University of Arizona investigated their use in three patients treated with the Novalis Body system, finding the use of implanted fiducials provided superior set-up as compared to bony fusion alone (23). A limitation to this study was the lack of final 3D verification of the type that our CT-on-rails system can provide – thus, the comparisons between bony fusion and marker fusion ultimately derived from ExacTrac software based calculation of true fiducial position – not an independent verification scan.

Thus, the most basic goal of this protocol is to incorporate a well-established practice (implanted gold fiducials) into our treatment delivery platform for spinal SBRT, allowing us to validate the robustness of our system, and, with increased confidence in the accuracy of treatment delivery, enhance clinical decision making.

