5.6 Set-up verification

On the day of treatment, patients will first be set up on the treatment table as per our standard practice. Once the patient has been positioned by the treatment team, the ExacTrac software will calculate couch correction based on bony fusion of kV images with the treatment planning CT scan. These couch corrections will be transmitted to the patient couch, and the ExacTrac software will re-verify. Next, the cone beam CT will be used to perform a verification scan. In-house 3D-3D matching software will be used to verify the position of the final treatment isocenter. This procedure represents our current clinical practice, and is unchanged for this protocol. The cone beam CT dataset will also provide independent, 6-dimensional information on the accuracy of the calculated couch correction.

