We will use descriptive statistics to summarize the demographic and clinical characteristics of patients enrolled in this study. We will similarly summarize Dmax, D5cc, central lumen dose, and full thickness dose for each patient group (defined above).

We will use the methods of Bland and Altman (43) to compare the positioning of the isocenter with respect to 6 directional orientations (superior-inferior, anterior-posterior, lateral-medial, pitch, roll, and yaw) using the implanted fiducial markers and using our standard practice for each patient group. We will similarly compare the 3-dimensional distance from the isocenter as calculated using the implanted fiducial markers and using our standard practice. We will also estimate these paired differences (fiducial – standard practice) with 95% confidence intervals, and we will estimate with 95% confidence intervals the correlation between the measures made using the fiducial markers and those made using standard practice. We will similarly analyze Dmax, D5cc, central lumen dose, and full thickness dose for each patient group.

We will tabulate adverse events by grade for each patient group.

Sample Size

We will test whether the paired difference (fiducial – standard practice) in 3-dimensional distance from the isocenter is significantly different from 0. A sample size of 10 patients in each patient group will give us 80% power to detect an effect size of 1 standard deviation with a 2-sided significance level of 0.05. A sample size of 10 patients will also give us 82% power to

detect a correlation between the 2 methods of estimating the position of the isocenter of at least 0.80 using a 2-sided significance level of 0.05. These sample size calculations were performed with nQuery Advisor ® 7.0 (Copyright © 1995-2007, Statistical Solutions, Saugus, MA).

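### Section 8 has no analysis of the cone beam CT residual after ExacTrac correction, and no use of the 1 mm / 2 degree tolerance, so set-up accuracy in Groups 5-7 has no planned result

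*Combined protocol and SAP*

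**What the plan says.** **The question.** Section 2.0 says that "it remains unclear whether new alignment technologies obviate the need for the latter step of 3D-3D verification" and presents the protocol as a response to this and related gaps. Section 2.1 lists it as the second of two questions that fiducials would help with, "thus allowing us to assess whether our current practice of final 3D-3D verification is necessary". Section 1.0 has no objective on dropping verification. The nearest is objective 1.2: "Characterize the six-dimensional set-up accuracy of the ExacTrac patient positioning system as applied to spinal SBRT".

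**The current aim.** Section 2.3 removes fiducials and enrols new patients to measure accuracy on the new linear accelerator. Section 5.1 puts them in Groups 5, 6 and 7, 10 patients each, without fiducials.

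**The tolerance.** Section 2.1 describes the check of the treatment position against the planning CT, "with tolerances for translation and rotational error of 1 mm and 2 degrees, respectively".

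**The data.** Section 5.6 has ExacTrac correct the couch and re-verify, followed by a cone beam CT: "The cone beam CT dataset will also provide independent, 6-dimensional information on the accuracy of the calculated couch correction".

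**The analysis.** Section 8.0 plans Bland-Altman methods on six axes, 95% confidence intervals for paired differences, a correlation with its interval, and one test of a mean: "We will test whether the paired difference (fiducial – standard practice) in 3-dimensional distance from the isocenter is significantly different from 0". On size: "A sample size of 10 patients in each patient group will give us 80% power to detect an effect size of 1 standard deviation". That test is two-sided at the 0.05 level. A second calculation gives 82% power for a correlation of at least 0.80. In all of these the contrast is fiducial against standard practice.

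**The concern.** Two things are missing. First, the quantity of interest in Groups 5-7 is the error that the cone beam CT still finds after the ExacTrac correction, and no analysis in Section 8 uses it. The contrast that Section 8 does analyse needs fiducials, so followed as written it gives no result on ExacTrac accuracy in these 30 patients.

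Second, replacing the word fiducial by cone beam CT would not be enough. Whether a check made on every patient adds anything depends on how often a single set-up fails it. A mean difference tested against 0 and a correlation do not measure that. Bland-Altman limits come closer, because they describe the spread of individual differences, but Section 8 gives no limit to hold them against.

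What is at stake is the weight of any later remark that 3D verification adds little. Section 2.1 itself cites earlier work in which a 2 mm shift cost more than 5% of tumor coverage and raised maximal organ-at-risk dose by more than 25%, so single large errors matter even where the average is near zero.

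**Working it through.** **1. The plan's own figures reproduce.** Inputs from Section 8.0: n = 10, effect 1 SD, two-sided 0.05.
- Paired t-test: 9 degrees of freedom, noncentrality √10 = 3.16, critical value 2.262. Power is 80.3% (plan: 80%).
- Correlation by Fisher's z: arctanh(0.80) × √7 − 1.96 = 2.907 − 1.960 = 0.947, and Φ(0.947) = 82.8% (plan: 82%).

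The sample-size arithmetic is not in dispute.

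**2. What a test against 0 says about single set-ups.** The documents give no SD in mm, so a range is assumed. Take signed residuals on one axis as normal with true mean 0. The test is then non-significant 95% of the time whatever the SD. The share beyond 1 mm is p = 2 × (1 − Φ(1/SD)). On at least one of three axes, assumed independent with equal SD, it is 1 − (1 − p)³.

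| Assumed SD (mm) | One axis | Any of three axes |
|---|---|---|
| 0.5 | 4.6% | 13% |
| 0.75 | 18% | 45% |
| 1.0 | 32% | 68% |
| 1.5 | 50% | 88% |

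These are illustrations, not estimates for this platform. They show that the same test result fits very different failure rates.

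**3. The planned endpoint is a 3D distance, not a signed axis value.** A difference between two distances can also hide disagreement. If one method puts the isocenter 1 mm to the left and the other 1 mm to the right, the difference in distance is 1 − 1 = 0, while the two positions lie 1 + 1 = 2 mm apart. Correlation fails in another way: a constant offset of any size leaves it at 1.

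**4. What the data can support if set against the tolerance.**
- *Proportion of patients out of tolerance.* With no failures in n patients, the exact one-sided 95% upper bound is 1 − 0.05^(1/n). For n = 10 it is 25.9%; for n = 30 (Groups 5-7 pooled) it is 9.5%. One failure in 30 gives 14.9%. With zero failures, excluding a 10% rate takes 29 patients and excluding a 5% rate takes 59.
- *Precision of bias and limits of agreement at n = 10.* The 95% half-width is 2.262/√10 = 0.72 SD for the mean and 2.262 × √(1/10 + 1.96²/18) = 1.27 SD for each limit.
- *Chance that the outer confidence limits of both limits of agreement lie within ±1 mm on one axis, true bias 0 (simulated):*

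| Assumed SD (mm) | n = 10 | n = 30 |
|---|---|---|
| 0.25 | 79% | >99% |
| 0.30 | 49% | 95% |
| 0.40 | 12% | 27% |
| 0.50 | 3% | 2% |

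The data can therefore inform the question. One group of 10 can do so only if residuals are small, and the pooled 30 do better.

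**The case against.** The strongest reply is that the trial promises less than this point assumes. No objective in Section 1.0 concerns dropping verification. The sentence in Section 2.1 is a background rationale for fiducials, which are gone. Sections 2.3 and 5.1 now aim only to describe accuracy, and Section 5.6 keeps the verification scan in place. The test against 0 was written for the other question, whether fiducials help, and no text says that a non-significant result would show verification to be redundant. All of this stands. It limits the point to a missing description, with no faulty decision rule alleged. It does not remove the point: the gap in Section 2.0 is still there, describing accuracy is the current aim, and Section 8 does not describe it for Groups 5-7.

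A reader might infer that Section 8 tests nothing but a zero mean difference. It does not support that reading: a correlation test is also powered, and Bland-Altman methods are planned on six axes.

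A reader might also take the words in Section 2.3 about an average difference near zero as proof that cancelling errors are being read as agreement. The same figure legend reports an RMS comparison, which does not cancel signed errors, and the topic there is fiducials against bony fusion.

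Finally, the tolerance is stated for the earlier CT-on-rails check, and the text does not say whether 1 mm is per axis or for the 3D vector. Stage 1 also mixes single- and multi-fraction patients (Section 5.5.1). These are fair cautions, and the fix has to settle them.

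**Conclusion.** The point holds in a limited form. Section 8 contains no analysis of the post-correction cone beam CT residual and makes no use of the 1 mm / 2 degree tolerance, and the positioning contrast that it does plan cannot be formed in Groups 5-7. Updating the comparator alone would leave the second half of the problem.

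A reader might go further and say that the trial sets out to decide on dropping verification, or that it is unable to answer the question. The documents support neither: the wording is to assess, no objective names such a decision, and the relevant scans are collected. What is absent is the planned analysis and a benchmark.

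On size, the upper bounds of 25.9% (0 of 10) and 9.5% (0 of 30) are exact and need only one independent set-up per patient. The pooled bound also treats the three groups as sharing one rate. The out-of-tolerance shares and the limits-of-agreement probabilities depend on assumed SDs and normality, and the three-axis shares on independence as well.

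**What to change.** In Section 8, for Groups 5-7:
- Make the cone beam CT residual after ExacTrac correction the analysed quantity, in place of fiducial minus standard practice.
- Report bias and limits of agreement on six axes, with 95% confidence intervals, against ±1 mm and ±2 degrees.
- Report the proportion of patients out of tolerance, by group and pooled, with an exact one-sided 95% upper bound.
- State whether the 1 mm applies per axis or to the 3D vector, and confirm that the tolerance given for CT-on-rails is the benchmark for cone beam CT.
- Use one set-up per patient, for example the first fraction, for the main proportion, and report all fractions in addition. Otherwise the proportion depends on the mix of single- and multi-fraction patients.
- State that any remark on the need for verification rests on that upper bound, not on a non-significant difference or a correlation, and that the best attainable bound is 25.9% in one group and 9.5% pooled.

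The cost is wording and slightly more analysis. No added scans, visits or patients are needed. The downside is a more modest conclusion.

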2.2 Normal organ tolerance to hypofractionated radiation

The use of SBRT has increased dramatically within the past decade (24) – in addition to emerging as a standard of care option for non-resectable Stage I/II non-small cell lung cancer (NSCLC, (25), SBRT has been applied to malignant disease at multiple body sites, including liver (26), prostate (27), adrenal (28), and spine. As a relatively young technology, robust

clinical data is not yet available on the tolerance of normal tissues to large dose hypofractionated radiation (e.g. 60 Gy in three fractions for NSCLC). Indeed, the normal tissue tolerance used on current prospective protocols are derived from a consensus of expert opinion (29), and not on rigorously acquired clinical data.

This paucity of data is particularly acute for the esophagus, which has not been a focus of analysis in prior single or multi-institutional trials. A review of the literature (Table 1) underscores this point, as multiple single institutional experiences do not specify their esophageal dose constraints, nor elaborate on the details of toxicity. While there are several ongoing multicenter trials of SBRT for lung and spine, the esophageal constraints are quite variable across trials (Table 2).

Table 1. Reported esophageal constraints and toxicities from single institution reports of SBRT. NS = not specified

Study	Target	Fractions	<5cc	Dmax	Esophageal toxicity
Yamada 2008 (15)	Spine	1	NS	NS	1 TE fistula
Fakiris 2009 (30)	Lung	3	NS	NS	None reported
McGarry 2005 (31)	Lung	3	NS	NS	None reported
Baumann 2009 (32)	Lung	3	NS	NS	4% G1-G2 esophagitis
Grills 2010 (33)	Lung	4-5	NS	NS	None reported
Chang 2007 (8)	Spine	3-5	15 Gy	21 Gy	1 case G3 dysphagia
Onishi 2007 (34)	Lung	1-22	Not constrained	Not constrained	1% G3 esophagitis

Table 2. Reported esophageal constraints and toxicities from multicenter trials using SBRT.

Study	Target	Fractions	<1cc	Dmax	Esophageal toxicity
RTOG 0236 (35)	Lung	3	NS	27 Gy	1/55 G3 GI, no esophageal tox.
RTOG 0618 (36)	Lung	3	NS	27 Gy	Results pending
RTOG 0631(12)	Spine	1	11.9 Gy	16 Gy	Results pending
RTOG 0813 (37)	Lung	5	NS	52.5 Gy	Results pending
ROSEL (38)	Lung	3	24 Gy	NS	Results pending

Overall, the current state of the clinical literature highlights the need for high quality data for esophageal toxicity in the setting of large dose hypofractionated radiation therapy. Taken together, these reports indicate that, in current practice, SBRT is exceptionally well-tolerated with respect to the esophagus, and suggest that current practice may reflect overly conservative esophageal dose constraints. In the setting of spinal SBRT, while primarily driven by the spinal cord tolerance, esophageal dose constraints can be another significant factor forcing clinicians to compromise CTV coverage for fear of inducing esophageal toxicity.

Interestingly, while a significant portion of SBRT data come from respiratory gated four dimensional (4D) CT based treatment of lung tumors, the question of how organ motion should be incorporated into setting dose constraints for normal tissues has been largely ignored. A prior

study of esophageal motion in 29 patients using 4D CT demonstrated a substantial degree of esophageal motion, noting that 9 mm and 8 mm margins respectively would have been necessary to incorporate all movement of the distal esophagus in the medio-lateral and dorso-ventral directions (39).

Given that the current state of SBRT practice thus relies on esophageal constraint parameters which a) may unnecessarily force compromise of CTV coverage through overly strict constraints and b) do not account for organ motion, the second major goal of this protocol is to employ our fiducial-enhanced, 4DCT based, treatment platform to prospectively collect high-quality data on esophageal dose tolerance through careful constraint relaxation.

